Protocol Title:

Double-Blinded Randomized Control Trial Comparing Liposomal Bupivacaine and Bupivacaine Hydrochloride in Transversus Abdominis Plane Blocks Prior To DIEP Flap for Breast Reconstruction

Protocol Version Date:

10/01/2018

NCT # 03700970

Principal Investigator:

[name] – Professor, Department of Plastic Surgery, Vanderbilt University Medical Center
[name]

Sub-Investigators:

[name] [name] – Assistant Professor, Department of Anesthesiology, Vanderbilt University Medical Center
[name] [name] – Professor, Department of Anesthesiology, Vanderbilt University Medical Center
[name] – Associate Professor, Department of Plastic Surgery, Vanderbilt University Medical Center
[name] – Department of Plastic Surgery, Vanderbilt University Medical Center

Background

Perioperative and postoperative analgesia is a high priority for patients undergoing plastic and reconstructive surgery. It is of particular interest in patients undergoing abdominally-based free flaps for breast reconstruction (e.g., deep inferior epigastric artery perforator flaps) that includes excision of abdominal skin and subcutaneous tissue since the majority of pain after these operations is derived from the abdominal donor site (Jablonka et al, PRS 2017). Although intravenous and oral opioids have been the mainstay of postoperative pain control for this patient population, they are associated with a number of detrimental effects that can delay recovery and increase length of hospital stay. For example, they can lead to nausea, vomiting, constipation, lethargy, cough suppression, confusion, and orthostatic hypotension (Pizzi et al; Pharmacotherapy 2012). By reducing these side effects, resumption of a normal diet and ambulation can be achieved faster, which can accelerate recovery. This in turn can lead to decreased length of hospital stay and its associated cost, as well as improvement in the perceived quality of life for this patient population.

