- 1) Pain control, as measured by a visual analog NPS number ranging from 0 (no pain at all) to 10 (worst pain ever) between the 2 groups. This will be evaluated immediately after surgery in the postanesthesia care unit (PACU), on the day of surgery and all subsequent postoperative days until discharge and on postoperative day 7. In the PACU patients will be asked about their current pain. For the inpatient postoperative days and postoperative day 7, patients will be asked to record their average, current, and maximum Numeric Pain Scale (NPS) score for the previous 24 hours
- 2) Time to first opiate use: time from end of surgery (i.e. patient went to recovery or ICU) until time of first opioid intake)
- 3) Time to return of bowel function: time from end of surgery (i.e. patient went to recovery or ICU)
- 4) Incidence of narcotic complications (i.e. nausea, vomiting, constipation, urinary retention, dizziness, etc.); defined as the number of occurrences of the complication per day for the first 7 days after surgery
- 5) Quality of life (QoL) as measured with:
Baseline (during consenting before surgery): WHODAS, QoR-15, PROMIS-29
0-7 days: QoR-15
Day 7 and 14: PROMIS-29
Day 30: PROMIS-29, WHODAS

Inclusion/Exclusion Criteria

Inclusion criteria will include:

- 1) age between 18-85 years
- 2) males or females
- 3) plastic surgery for abdominally-based free flap breast reconstruction.

Exclusion criteria will include:

- 1) those not candidates for TAP blocks due to allergies to the medications (e.g., bupivacaine)
- 2) those with anatomic contra-indications to performing a TAP block
- 3) those unwilling to participate in follow-up assessments
- 4) vulnerable populations
- 5) chronic pain or associated diagnosis

Enrollment/Randomization

Patients undergoing abdominally-based free flap breast reconstruction under general anesthesia will be randomized to receive a TAP block with either liposomal bupivacaine or plain bupivacaine to determine if narcotic requirements and/or pain control is better achieved with one of the above methods. Patients in this study will be recruited in the plastic surgery outpatient clinics. No advertising will be done and there will be no recruitment tactics.

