Patients eligible for the study will be seen by the participating attendings at Vanderbilt University Medical Center, or one of their associates. The patient will be told about the study and given an opportunity to read the consent. If they wish to participate, they will be asked to sign the consent.

Participants will be randomized to receive liposomal bupivacaine or plain bupivacaine in a permuted block fashion, in block of sizes 2 or 4. For each block, block size will be selected uniformly at random. This method of randomization ensures balance between groups following every second or fourth allocation. The patients will be randomized after providing written informed consent in the outpatient clinic. Following randomization, the plastic surgeons performing the surgery and assessments will be blinded to study treatment arm. Patients will also be blinded to the study treatment arm. The anesthesia team and some of the ancillary research staff will not be blinded to study treatment arm.

Study Procedures

Patients randomly assigned to the liposomal bupivacaine group or plain bupivacaine group will receive this intervention intra-operatively prior to the initiation of surgery.

Local analgesia (TAP blocks) will be administered under ultrasound guidance in the operating room after the patient is intubated and under general anesthesia. Transfascial injections will be performed by the anesthesiologist using an epidural needle. Under sterile conditions and ultrasound guidance, the fascial plane between the internal oblique and transversus abdominis muscles (muscles of the abdominal wall) will be identified at the anterior axillary line, midway between the costal margin and iliac crest. The epidural needle will be inserted through the skin to the appropriate fascial plane, and the local anesthetic will be injected in that plane. Then the needle will be removed and discarded, and the patient will be prepped and draped to start the surgery.

Liposomal bupivacaine group: 20mL of Exparel® 1.3% mixed with 20mL of 0.25% bupivacaine, for a total of 40mL of local anesthetic mixture, 20mL to be injected on each side.

Regular bupivacaine group: 20mL of 0.25% bupivacaine injected on each side.

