Study Title: Double-Blinded Randomized Control Trial Comparing Liposomal Bupivacaine and Plain Bupivacaine in Transversus Abdominis Plane For Deep Inferior Epigastric Artery Perforator (DIEP) Flap Breast Reconstruction

NCT # 03700970

Document date: October 1, 2018

Statistical Analysis

Patient characteristics were summarized as appropriate, using mean (standard deviation [SD]) and median (25th-75th interquartile range [IQR]) for quantitative variables and counts (percentages) for qualitative variables. Unadjusted comparisons of patients between the plain bupivacaine group and the liposomal bupivacaine group were performed using Wilcoxon test or Pearson chi-square test. The effect of the study intervention on daily oral opioid intake in oral morphine equivalents (OME) was examined using linear mixed effects regression model, adjusting for post-operative day (as a categorical variable), intervention status (plain bupivacaine/ liposomal bupivacaine), and their interaction. Since there were repeated measurements of OME for 7 post-operative days, a random intercept indexed by subject number was used in the linear mixed effects regression model. All analyses were performed using the R Programming Language 3.3.0 (R Foundation for Statistical Computing, Vienna, Austria). P<0.05 was considered a statistically significant difference.

Sample size calculations were based on demonstrating superiority of the TAP block with liposomal bupivacaine. A simulation-based power analysis was used to evaluate statistical power under the following assumptions: 1) use of linear mixed effects regression after log transformation of the opioid intake outcome, 2) average opioid consumption on days 0, 1, 2, and

3 is 30, 90, 70 mg mEq under standard of care, 3) use of liposomal bupivacaine will result in a 20% reduction in opioid consumption at each study day, and 4) the between- and within-subjects coefficients of variation are 20% and 60%, respectively (these values are based on standard of care data from our institution). Thus, the minimum-detectable difference is a 20% reduction in average opioid consumption at each study day. Under these assumptions, 60 participants are needed to achieve 80% power.

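### The primary model omits planned laterality and mastectomy timing, which eligibility leaves open; adjusting for them would be a cheap gain in precision, not the repair of a bias

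*Protocol*

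**What the plan says.** **Eligibility.** Inclusion criterion 3 of the protocol is the only one that describes the operation: "plastic surgery for abdominally-based free flap breast reconstruction". It places no limit on one or both breasts, or on whether mastectomy is done the same day. None of the exclusion criteria does either.

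**Randomization.** Under Enrollment/Randomization, patients are allocated "in a permuted block fashion, in block of sizes 2 or 4", with no stratification factor. The protocol adds that "This method of randomization ensures balance between groups following every second or fourth allocation". That is balance in numbers per arm, not in type of operation. Patients are randomized after consent in the outpatient clinic.

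**Primary model.** The SAP fits a linear mixed model to daily opioid intake, "adjusting for post-operative day (as a categorical variable), intervention status (plain bupivacaine/ liposomal bupivacaine), and their interaction", and "a random intercept indexed by subject number was used in the linear mixed effects regression model". No baseline covariate is named.

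**Baseline comparison.** "Unadjusted comparisons of patients between the plain bupivacaine group and the liposomal bupivacaine group were performed using Wilcoxon test or Pearson chi-square test". Nothing says that an imbalance found this way would enter the model.

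**Data collected.** The list under Follow up and Record Retention names demographics and outcomes, but no feature of the operation.

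**The concern.** The primary endpoint is total postoperative opioid intake, whatever the source of the pain. Both study drugs are injected into the abdominal wall. The protocol's Background says that "the majority of pain after these operations is derived from the abdominal donor site": most of the pain, not all of it. A second breast or a same-day mastectomy could plausibly add opioid need in both arms that has nothing to do with the comparison of the two drugs.

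If so, the planned operation predicts the outcome, is settled before treatment, and is left out of both the allocation and the model. Two things follow. Variance that could be explained stays in the standard error. And with 30 patients per arm, an uneven split that appears in the baseline table has no prespecified answer, so any later adjustment would be post hoc.

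**Working it through.** **Inputs from the SAP.** 60 patients (30 per arm, 1:1 inferred from the blocks); a 20% reduction, so δ = −ln(0.8) = 0.2231 on the log scale; between-subject CV 20%, so b = ln(1 + 0.20²) = 0.0392; within-subject CV 60%, so w = ln(1 + 0.60²) = 0.3075. The power text names 4 days (0 to 3). The protocol's primary aim covers days 0 to 7, which is 8 daily values. Both k = 4 and k = 8 are shown.

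**Inputs assumed.** Prevalence of the feature (half, or 20 of 60), its ratio on opioid use (1.2 to 1.25), and the share of b that adjustment removes (10% to 30%).

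**1. The plan's own figure.** With balanced data, the treatment effect averaged over days is a comparison of subject means of k log values. SE = √[2(b + w/k)/30] and power = Φ(δ/SE − z).
- k = 4: SE = √[2(0.0392 + 0.0769)/30] = 0.0880. One-sided 5% gives power 81.4% and N = 58, which agrees with the stated 60 and 80%. Two-sided 5% gives 71.8% and N = 74.
- k = 8: SE = √[2(0.0392 + 0.0384)/30] = 0.0720. Two-sided power is 87.3%.

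The SAP does not state sidedness. Two-sided figures are used below.

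**2. How likely is a 20-point gap?** The number of patients with the feature in one arm of 30 is hypergeometric. The probability of a difference of at least 20 percentage points is 0.196 if 30 of 60 have the feature, and 0.170 if 20 of 60 do.

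**3. What a 20-point gap does to the estimate.** Shift = 0.2 × ln(ratio).

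| Ratio | Shift | Share of δ | In SEs, k = 4 | In SEs, k = 8 | A true 20% reduction reads as |
|---|---|---|---|---|---|
| 1.2 | 0.0365 | 16% | 0.41 | 0.51 | 17.0% or 22.9% |
| 1.25 | 0.0446 | 20% | 0.51 | 0.62 | 16.3% or 23.5% |

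**4. Does the assumed ratio fit the SAP's variance?** At 50% prevalence a feature contributes 0.25 × ln(ratio)².
- 1.2: 0.0083, which is 21% of b.
- 1.25: 0.0124, which is 32% of b.
- 1.5: 0.0411, which is 105% of b. This is more than all the between-patient variation the SAP allows, so ratios of that size are not used.

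**5. What adjustment gains.** SE ratio = √[(b(1 − R²) + w/k)/(b + w/k)].

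| k | R² | SE ratio | Two-sided power |
|---|---|---|---|
| 4 | 0 | 1.000 | 71.8% |
| 4 | 0.10 | 0.983 | 73.3% |
| 4 | 0.30 | 0.948 | 76.3% |
| 8 | 0 | 1.000 | 87.3% |
| 8 | 0.10 | 0.974 | 88.9% |
| 8 | 0.30 | 0.921 | 92.0% |

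The standard error falls by 2% to 5% (k = 4) or 3% to 8% (k = 8), and power rises by about 1.5 to 4.7 points. The gain is limited because b makes up only 0.0392/0.1161 = 34% of the variance of a 4-day mean.

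**6. Validity.** In a simulation with ratio 1.3, 4 days and a two-sided test, the unadjusted estimate averaged −0.223, equal to the true effect. Type I error was 0.047 unadjusted and 0.048 adjusted. Power rose from 0.70 to 0.76.

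**The case against.** A reader might infer that an uneven split would bias the trial, or pass for a drug effect with nothing in the analysis to allow for it. The documents do not support that. Allocation is random, so the unadjusted estimate is right on average. The subject intercept absorbs differences between patients and carries them into the standard error, and step 6 bears this out. A 20-point gap is also only about half a standard error with 4 daily values. This objection stands: the loss is in precision and in the reading of one realised result, not in validity.

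Three further objections limit the point.
- Neither document mentions laterality or mastectomy timing. That both kinds of case will be enrolled is inferred from the criterion's silence, and their effect on opioid use is assumed. The Background's remark on donor-site pain suggests that the effect may be modest.
- The SAP takes its CVs from the institution's standard-of-care data. If those patients had a similar mix, this variance is already in the sample size, and adjustment adds power rather than making good a shortfall.
- A ratio of 1.5 would give a shift of 36% of the planned effect, but step 4 shows that it conflicts with the SAP's own variance.

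One might also argue from the SAP title, "For Deep Inferior Epigastric Artery Perforator (DIEP) Flap Breast Reconstruction", that enrolment should be confined to DIEP flaps. The background, aim, criterion and enrollment text all use the wider term, with DIEP given as an example. The mismatch is editorial, and narrowing entry would cost recruitment.

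What survives is that the plan leaves a cheap gain unused.

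**Conclusion.** The point holds as a modest improvement in precision. Eligibility leaves laterality and mastectomy timing open, allocation is unstratified, and the primary model has no baseline surgical covariate; all three can be read directly in the documents. The primary comparison remains valid as written.

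The size rests on assumptions. At 50% prevalence and a ratio of 1.2 to 1.25, there is about a one-in-five chance of a gap of at least 20 points. A gap of 20 points moves the log effect by 16% to 20% of the planned effect (0.4 to 0.5 standard errors with 4 values). If adjustment removes 10% to 30% of the between-subject variance, the standard error falls by 2% to 8% across the two day counts, and two-sided power rises by about 1 to 5 points. If the features have little effect on opioid use, or nearly all patients have the same type of operation, the gain shrinks towards nothing.

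**What to change.** Add one sentence to the SAP's primary model: include planned unilateral versus bilateral reconstruction and planned immediate (same-day mastectomy) versus delayed reconstruction as fixed covariates. Take both from the planned procedure recorded at consent, before randomization. A record made later, even if before the block, could postdate allocation. Keep the planned category if the operation changes.

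The cost is two degrees of freedom in a 60-patient model and two REDCap fields. No visits or patients are added, and eligibility does not change.

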Local analgesia, in the form of transversus abdominis plane (TAP) block that is administered in the operating room prior to the incision under ultrasound guidance, has been advocated to provide improved analgesia in the perioperative and postoperative periods. This is a promising approach that can decrease or even eliminate the need for narcotics in the postoperative period. This is a standard procedure at VUMC, and part of the Enhanced Recovery Pathway, for patients undergoing abdominally-based free flap breast reconstruction. However, there is debate regarding the best local anesthetic for these purposes. Liposomal bupivacaine has been used widely and is believed to provide adequate analgesia for more than 48 hours after surgery. On the other hand, plain bupivacaine is significantly cheaper and has also been shown to have promising and lasting analgesic results. To date, there are not randomized trials comparing the two local analgesics in a well-defined group of plastic surgery patients in general and also specifically in patients undergoing abdominally-based free flap breast reconstruction.

Rationale and Specific Aims

This study is designed to compare the efficiency of TAP blocks using liposomal bupivacaine versus plain bupivacaine that is administered in the operating room under ultrasound guidance prior to the incision in patients undergoing abdominally-based free flap breast reconstruction.

The ***primary aim*** of the study will be to compare the amount of supplemental postoperative narcotic analgesia (both intravenous and oral) required by the study groups in oral morphine equivalents from postoperative days 0 to 7. The amount of postoperative analgesia will be documented daily until postoperative day 7. It will be obtained from the medical records during hospitalization, and with daily phone calls after the patients get discharged with instructions to document this data daily.

The *secondary aims* will be:

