Local anesthetic toxicity or nerve injury will be considered serious adverse events. Also allergic reactions to the local anesthetic will be considered adverse events. These patients will be withdrawn from the study and appropriate treatment will be instituted. The anesthesia care team will identify such an event and report it.

Statistical Considerations

Sample size calculations were based on demonstrating superiority of the TAP block with liposomal bupivacaine.

The sample size calculation for the oral morphine equivalent requirements was based on one of our previous studies on Enhanced Recovery Pathway for free flap breast reconstruction. Calculations showed that randomizing 60 patients will obtain 80% power to detect a difference between the two groups.

Privacy/Confidentiality Issues

Collected data will be stored in a password protected REDCap™ database with sole access delineated by the investigators and study personnel of the study.

Follow up and Record Retention

The data will be extracted from the EMR via of EPIC (eStar) and entered in a RedCap™ database. Paper copies of the surveys will be kept in a locked cabinet by the investigators of the study until study completion of all data analysis and then subsequently securely destroyed.

Collected data will include demographics, amount of supplemental postoperative narcotic analgesia both intravenous and oral, visual analog pain scale, time to return of bowel function, time to first opiate use, incidence of narcotic complications, and Quality of Life. Some of these variables will be collected at several times points as described above.

Records will be retained for 6 years following the study completion.

References

Practice guidelines for acute pain management in the perioperative setting. A report by the American Society of Anesthesiologists Task Force on Pain Management, Acute Pain Section. *Anesthesiology*. 1995; 82(4):1071-81.

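### The plan does not provide for preoperative opioid use: eligibility does not screen for it, its recording and adjustment are not planned, and no rule separates a habitual dose from the primary opioid outcome

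*Protocol*

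**What the plan says.** **Eligibility.** The protocol's Inclusion/Exclusion Criteria list five exclusions. Four concern allergy, anatomy, follow-up and vulnerable populations. The fifth, "chronic pain or associated diagnosis", is the only one that bears on opioids. It does not define which diagnoses count as associated, and it does not name opioid use, tolerance or maintenance therapy. No inclusion criterion asks for opioid-naive patients.

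**Outcome.** Under Rationale and Specific Aims, the primary aim is to "compare the amount of supplemental postoperative narcotic analgesia (both intravenous and oral) required by the study groups in oral morphine equivalents", over postoperative days 0 to 7. On the source of the data, the protocol says: "It will be obtained from the medical records during hospitalization, and with daily phone calls after the patients get discharged". The SAP describes the analysis this way: "The effect of the study intervention on daily oral opioid intake in oral morphine equivalents (OME) was examined using linear mixed effects regression model". Neither document has a rule for a dose that the patient was already taking.

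**Data.** The list under Follow up and Record Retention begins "Collected data will include demographics, amount of supplemental postoperative narcotic analgesia both intravenous and oral" and goes on to pain scores, bowel function, time to first opiate, narcotic complications and quality of life. The baseline assessments under the secondary aims are WHODAS, QoR-15 and PROMIS-29. Neither place names preoperative opioid use.

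**Allocation and model.** Randomization uses permuted blocks of 2 or 4 and names no stratification factor. The SAP model contains day, arm, their interaction and a random intercept per patient.

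**Planning variability.** The SAP assumes that "the between- and within-subjects coefficients of variation are 20% and 60%, respectively", from the institution's standard-of-care data.

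**The concern.** Preoperative opioid use is an obvious candidate predictor of how much opioid a patient takes after surgery, yet eligibility, data capture, allocation and analysis all leave it out. A patient on maintenance therapy, or still taking opioids after a recent operation, can be enrolled if no pain diagnosis is recorded. If that patient's usual dose goes into the daily total, part of the outcome is unrelated to the operation and to the block.

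The random intercept does not solve this. It attributes the excess to between-patient variance, and that variance is what limits the precision of the comparison between arms. A baseline covariate would explain part of it; the intercept only accounts for it. In a 60-patient trial that seeks a 20% reduction, a few such patients can also fall unevenly between the arms.

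**Working it through.** **Inputs from the SAP:** 60 patients (30 per arm); 20% reduction each day; between- and within-patient CV 20% and 60%; control means 30, 90 and 70 mg; P<0.05, sidedness not stated.

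**Inputs assumed, because the documents are silent:** the share of patients with prior use and their daily dose.

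**1. The plan's own figure.** On the log scale:
- between-patient variance b = ln(1 + 0.2²) = 0.0392
- within-patient variance w = ln(1 + 0.6²) = 0.3075
- target δ = −ln(0.8) = 0.223

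For a patient's mean over k days, SE = √[2(b + w/k)/30]. With k = 4 (days 0 to 3), SE = √[2(0.0392 + 0.0769)/30] = 0.088 and δ/SE = 2.54. Power is Φ(2.54 − 1.645) = 81% one-sided, which reproduces the stated 60 patients (N = 58 for 80%). Two-sided it is Φ(2.54 − 1.96) = 72% (N = 74). Two-sided with six days also reproduces the figure (82%, N = 58). The point does not depend on which was used; two-sided values follow.

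**2. One user.** The mean of 30, 90 and 70 is 63.3 mg/day, so the target is 0.2 × 63.3 = 12.7 mg/day. Assume a habitual 50 or 100 mg OME/day on top.
- Raw scale: the arm mean moves by 50/30 = 1.7 or 100/30 = 3.3 mg/day, which is 13% or 26% of the target.
- Log scale: s = ln(113.3/63.3) = 0.58 or ln(163.3/63.3) = 0.95. Divided by 30 this is 0.019 or 0.032, which is 9% or 14% of 0.223.

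Both scales matter, because the SAP mentions a log transformation only in its sample-size paragraph.

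**3. Two users among 60 (assumed).** With p = 1/30, the added between-patient variance is p(1 − p)s², so b rises from 0.039 to 0.050 or 0.068.

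| Days averaged | No users | Two at 50 mg | Two at 100 mg |
|---|---|---|---|
| 4 | 72% | 68% | 62% |
| 8 | 87% | 83% | 75% |

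**4. Simulation with a covariate.** A constant habitual dose, unaffected by the block, was added for a random share of patients. Patient-mean log OME was then compared with and without a prior-use term. The four-day means were 30, 90, 70 and, by assumption, 70.

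| Share and dose (assumed) | Power, unadjusted | Power, adjusted |
|---|---|---|
| None | 71% | – |
| 5%, 20 mg/day | 67% | 69% |
| 10%, 40 mg/day | 55% | 70% |
| 20%, 60 mg/day | 35% | 66% |

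Over eight days (later means assumed 40, 30, 20 and 20), power is 86% with no users. At 10% and 40 mg/day it is 55% unadjusted and 84% adjusted. Without the log transformation, the four-day case at 10% and 40 mg/day goes from 61% to 50%. Type I error stays nominal, at about 0.025 per tail. All users were given the same dose, which favours the adjusted analysis somewhat.

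**5. Chance imbalance.** With six users among 60 split 30:30, a division of 5:1 or more extreme has hypergeometric probability 0.19.

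**The case against.** Several stronger readings are tempting, and the documents do not support them.

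- *A habitual dose is counted in the outcome.* A reader might infer this from the SAP's daily intake. But the protocol calls the outcome supplemental, and a home dose is arguably not supplemental. What can be said is that no rule settles it.
- *Prior users cannot be identified later.* Study data are extracted from the electronic record, where a medication history may well be found. The data list says what will be included without saying that it is complete, and the SAP does not itemise its patient characteristics. What is missing is planned collection and a prespecified adjustment.
- *The trial was sized for a homogeneous population.* The CVs come from standard-of-care data, and nothing says that prior users were removed from them. If some were included, part of this variance is already in the 20%, and the losses shown would be overstated.
- *The comparison is biased.* Assignment is randomized, and the simulated type I error is nominal.

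The size is also open to challenge. The doses and shares are assumptions, and the chronic pain exclusion probably removes many users. One user moves the log-scale contrast by 0.019 to 0.032 against an SE of 0.088, or about 0.2 to 0.4 SE, which is within ordinary sampling noise. Broad eligibility is a legitimate choice in a randomized comparison.

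All of this stands, and it limits the point to precision of unknown size. It does not answer why an inexpensive baseline predictor of the primary outcome is left out, or how a habitual dose is to be counted.

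**Conclusion.** The gap is real and worth closing, as an improvement in precision and clarity. Patients who use opioids without a pain diagnosis are eligible. The documents plan neither to record that use nor to adjust for it, and they do not say whether a habitual dose belongs in the OME total.

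The cost in power could be nil, if no users enroll or if their usual dose is left out. It could be about 4 to 10 percentage points with two users among 60 at 50 to 100 mg/day over four days, or about 16 points with 10% of patients at 40 mg/day. These figures rest on assumed shares and doses, on the SAP's CVs describing patients without prior use, and on the habitual dose being counted in full. Under those assumptions, a prior-use covariate recovers most of the loss.

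**What to change.** 1. Extract preoperative opioid use (yes/no and OME per day) from the medical record into REDCap for every patient before surgery.
2. Add it as a prespecified baseline covariate in the primary mixed model.
3. State in the SAP how a habitual dose enters the daily OME total, so that the protocol's supplemental use and the SAP's daily intake mean the same thing.
4. Add a sensitivity analysis that leaves out prior users.

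The cost is one data field, one model term, one sentence and one extra analysis. The gain is small if few users enroll.

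Leave the eligibility criteria as they are. A new exclusion would change the target population. A criterion based on a fixed window before surgery might also not be assessable when it is needed, because consent and randomization take place in the outpatient clinic and the protocol gives no interval to surgery. Recording and adjusting recovers most of the simulated loss without either problem.
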